5.4 Adverse Event Reporting Requirements

The adverse events to treatment will be collected from the hospital records obtained from the patients induction period and also follow up at the treating physician's office. An AE log need not be maintained since this study will not include any new drugs. The complications from treatment will be noted in the database and will be used for analysis of outcomes. The only SAE that has to be reported is death.

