7.3.2 Secondary Objectives

Using the method of Kaplan-Meier, overall survival (OS) data will be described. The median OS and one-year OS rate will be estimated and 95% CI will be provided.

We confirm that the primary objective is to assess one-month mortality rate among all cases. Secondary analysis will involve evaluating outcome data in NCORP and academic sites separately. We clarified this further in Section [7.2](#). Overall the expected one-month mortality rate is in the range of 10-15% across all patients as well as in two subgroups of NCORP and academic sites.

With 200 (180 eligible) patients, we expect to build a confidence interval not wider than 11% for the expected one-month mortality rate of 10-15%. With 140 (126 eligible) cases from NCORP sites, the confidence interval for the one-month mortality rate will be not be wider than 13%.

For the safety endpoints, the severity and duration of coagulopathy, bleeding, infections and differentiation syndrome will be measured based on the CTC version 4.0. Analysis of the safety data will be mostly descriptive. The proportion of patients with the worst degree toxicity of grade 3 or higher will be assessed and presented with 95% CI. The length of hospital stay is defined as a period between the discharge and admission dates for the first hospitalization. For patients with no hospitalization, this will be defined as 0. To assess the associations between the length of hospital stay and toxicity measures (bleeding, infections, differentiation syndrome), each toxicity measures will be dichotomized as "mild" vs. "severe" and the length of hospital stay will be compared using the two-sample t-test.

The time from diagnosis and initiation of treatment will be assessed and dichotomized as "short" vs. "long" using the median value. One-month mortality rate will be compared in these two groups (short vs. long) using the Fisher's exact test. Overall-survival will also be

compared in these two groups using the logrank test. In this analysis, the time of diagnosis will be determined by both: i) confirmed diagnosis date and ii) date of suspicious APL. The dichotomized value of long vs. short based on the both times will be evaluated. Similarly the one-month morality rate and overall survival between the lead institutions and NCORP community centers will be compared. For all comparisons, two-sided p-values will be reported.

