Appendix I

Acute Promyelocytic Leukemia Treatment Guidelines

Developed at Georgia Regents University, August 2013 Revised May 2017

AUTHORS: [name] [contact] Office: [contact]
[name] [contact] Office: [contact]

WORK-UP

BASELINE

- Chest X-ray
- Echocardiogram and EKG
- PICC line placement – NO central lines in chest or neck or invasive procedures (bronchoscopy, spinal tap, endoscopy)
- Bone marrow examination (aspirate, biopsy, flow, cytogenetics, FISH for t15:17, PCR for PML-RAR α). Day 14 marrow is **NOT** necessary.

DAILY

- CBC, CMP, PT, PTT, fibrinogen **TWICE DAILY** until lab & clinical coagulopathy is resolved. CMP daily and twice a day as dictated by clinical condition.
- D-dimer **ONCE DAILY** for **ENTIRE** hospitalization.

PREVENTION/TREATMENT OF COAGULOPATHY

- Intracranial, pulmonary and GI hemorrhages are frequent
- Risk of hemorrhage is ↑ with the presence of any of the following - active sites of bleeding, ↓ fibrinogen, ↑ D-dimers, ↑ PT & PTT, ↑ WBC, ↑ peripheral blasts, renal failure and poor performance status;

Rev. Add2

- **Keep platelets above 50,000 (until resolution of DIC)**
- If there are any active sites of bleeding on presentation (e.g., needle sticks, bone marrow biopsy sites,), and prolonged PT/PTT), give 4 units of fresh frozen plasma (FFP) at the start of ATRA and chemotherapy. **CONTINUE FFP support TWICE A DAY** until clinical bleeding resolves.

Rev. Add2

- **Keep fibrinogen above 150.** Use 10 units of cryoprecipitate if < 150 (until DIC resolves).
- When clinical & lab coagulopathy is resolved, blood product support is per standard guidelines.

→ APL IS A MEDICAL EMERGENCY - START ATRA ASAP ←

PREVENTION/TREATMENT OF APL DIFFERENTIATION SYNDROME

Differentiation Syndrome-symptoms are – dyspnea, unexplained fever, ↑ weight, peripheral edema, unexplained hypotension, acute renal failure, CHF, pleuro-pericardial effusions, and interstitial pulmonary infiltrates.

- Daily weights - **BEDSIDE SCALES ONLY**
- Keep I/O matched – **METICULOUSLY**

Rev. Add2

- Diuretics if increase in fluid retention or weight.
- Prednisone 0.5 to 1 mg/Kg in all patients for 2 weeks as prophylaxis starting on day 1 followed by a taper.
- Increase Dexamethasone to 10 mg IV BID from the prophylactic dose above, if onset of DS symptoms.
- If WBC > 10,000, dexamethasone 10 mg IV bid could be started on day 1 before initiating ATRA.

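### The t-test of hospital stay by toxicity severity in Section 7.3.2 cannot be interpreted: the stay helps decide who is classed severe, and in-hospital death cuts it short

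*Combined protocol and SAP*

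**What the plan says.** The outcome is set in Section 7.3.2: "The length of hospital stay is defined as a period between the discharge and admission dates for the first hospitalization". The next sentence adds: "For patients with no hospitalization, this will be defined as 0". The purpose is given as "To assess the associations between the length of hospital stay and toxicity measures", the toxicities being bleeding, infections and differentiation syndrome. Each is reduced to mild or severe, and then "the length of hospital stay will be compared using the two-sample t-test". Two-sided p-values are promised for all comparisons.

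Section 7.3.2 does not give the grade that separates mild from severe in this comparison, the period over which toxicity counts, or how a patient who dies in hospital is handled.

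On the source of toxicity data, Section 5.4 says that adverse events will be "collected from the hospital records obtained from the patients induction period and also follow up at the treating physician's office". It does not require an adverse-event log. Appendix I ties part of the monitoring to admission, for example "D-dimer ONCE DAILY for ENTIRE hospitalization". The study calendar in Section 6 has a baseline column only, so no toxicity assessment is scheduled after discharge.

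**The concern.** A t-test of an outcome between two groups assumes that membership of the groups does not depend on the outcome. Here it does, in three ways.

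- **Time at risk.** A patient discharged on day 14 has had fewer inpatient days than one discharged on day 35 in which a severe event could occur and be recorded. This is time-dependent (immortal-time) bias, and it pushes the difference upwards.
- **Zero stays.** A patient never admitted has no inpatient record and will probably be classed mild, with a stay of 0. This also pushes upwards.
- **Death.** Section 1.1 names bleeding, differentiation syndrome and sepsis among the causes of early death. A patient who dies of one of them in the first week is severe with a very short stay. This pushes downwards.

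A reader would take a significant result to mean that severe toxicity lengthens admission. The same result could arise with no such effect, and a real lengthening could be hidden.

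**Working it through.** The plan has no expected stay, standard deviation, toxicity rate or power for this comparison, so there is no figure of its own to reproduce.

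**Inputs from the documents.** 180 eligible patients (7.2). Expected one-month mortality 10-15% (7.3.2). In the Swedish registry 23 of 30 early deaths, 77%, fell in the first week (1.1). Hemorrhage accounted for 41% to 66% of early deaths in the studies in the Section 1.1 table that report it.

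**Assumed inputs.** Stay: lognormal, mean 28 days, SD 10; a second set-up uses a gamma distribution, mean 28, SD 9 (range 5-15). Severe toxicity: 30% (range 20-40%). Onset: constant hazard, or early (exponential, mean 7 days). Test level: two-sided 5%. Toxicity has no effect on stay except in the last step.

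**Step 1: why stay drives the label.** With a constant hazard h and nothing recorded after discharge, P(severe | stay L) = 1 - exp(-hL). Setting this to 30% at L = 28 gives h = -ln(0.70)/28 = 0.0127 per day. Then:
- L = 0: 0%
- L = 14: 1 - 0.70^0.5 = 16%
- L = 28: 30%
- L = 42: 1 - 0.70^1.5 = 41%

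If onset is early, 1 - exp(-14/7) = 86% of the events have occurred by day 14, so stay has much less influence.

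**Step 2: rejection with no true effect and no deaths.**

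| Scenario | Severe minus mild (days) | Rejection |
|---|---|---|
| Constant hazard, no capture after discharge, lognormal | +4.1 | 71% |
| Same, plus 5% zero stays | | about 90% |
| Constant hazard, no capture, gamma, 20-40% severe | +3.2 to +3.5 | 46-73% |
| Same, 30% severe, SD 5 to 15 | +1.0 to +8.9 | 24-95% |
| Constant hazard, half captured, gamma | +1.4 to +1.8 | 15-26% |
| Constant hazard, all captured, gamma | +0.2 | about 5% |
| Early onset, no capture, gamma | +0.4 to +0.5 | 5-7% |

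Capture after discharge removes the bias only if toxicity is counted over the same period for everyone. In the lognormal set-up, full capture to day 30, with in-hospital events after day 30 still counted, rejects in 24%; a fixed 30-day window brings this to 5%. Early onset with 5% zero stays rejects in 19-26% (mean 28, SD 10 to mean 21, SD 14).

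**Step 3: add deaths.** Gamma set-up, 30% severe, no capture after discharge, 10% and 15% mortality, mean time to death about 7 days, still no effect of toxicity on discharge:

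| Share of deaths recorded as that toxicity | Constant hazard (days) | Early onset (days) |
|---|---|---|
| 41% | +1.4, +0.7 | -1.4, -2.1 |
| 66% | -0.7, -2.2 | -3.2, -4.5 |
| 100% | -3.3, -5.7 | -5.4, -7.5 |

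In the constant-hazard 100% row the test is significant in the negative direction in 52% and 89% of trials.

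**Step 4: add a real effect.** If severe toxicity truly adds 7 days, with early onset, half capture, 15% mortality and 66% of deaths recorded as that toxicity, the expected observed difference is +0.3 days.

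**The case against.** A reader might go further and infer that toxicity is looked for only in hospital and that the test must therefore come out positive. The documents do not support this. Section 5.4 also draws on office follow-up, so closer detection in hospital is an inference from Appendix I and the baseline-only calendar, not a stated rule. Nor is a constant hazard established. The Swedish registry's week-one deaths, mainly from bleeding, and the differentiation-syndrome prophylaxis from day 1 in Appendix I both suggest early risk, and with early onset and no zero stays the upward bias nearly vanishes. Once deaths are included the sign can reverse. These points stand, and they limit the claim to an uninterpretable test of unknown net direction.

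It can also be said that the analysis matters little. Length of stay is not among the objectives in Section 2.2 or the endpoints in 7.1, the plan speaks only of associations, and it calls the safety analysis mostly descriptive. No error rate is stated for this test. That limits the importance of the point. It does not rescue the method: 7.3.2 prescribes a formal test with a p-value, and opposing biases of unknown size do not cancel reliably.

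**Conclusion.** The concern holds in limited form. As planned, the t-test cannot separate an effect of toxicity on stay from the effect of stay on being classed severe, or either from shortening of the stay by death. With no true effect and no deaths, rejection runs from about 5% (early onset, or complete capture over a common period) to about 70% (constant hazard, no capture after discharge), and about 90% if 5% of stays are also zero. With 10-15% mortality the difference ranges from about +1.4 to -7.5 days in the scenarios shown.

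These sizes rest on assumed distributions of stay and onset, an assumed toxicity rate and an assumed zero-stay share; none is in the documents. The conclusion itself rests only on what 7.3.2 omits: a toxicity window, time-dependent handling and a rule for in-hospital death. The one-month mortality endpoint and the sample size are untouched.

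**What to change.** In Section 7.3.2, replace the t-test with a cause-specific hazard model for time from admission to live discharge among hospitalised patients. Enter severe toxicity as a time-dependent covariate from its onset date and treat in-hospital death as a competing event. State the grade that defines severe and the period over which toxicity counts.

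A simpler alternative is a landmark analysis. Classify toxicity up to a fixed early day, then compare time to live discharge among patients alive and in hospital on that day, with later deaths as competing events. In the lognormal set-up without deaths, a day-7 landmark rejected in 4-5% of trials.

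Under either version, leave never-hospitalised patients out of the comparison and describe them separately.

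The cost is revised SAP text and slightly more analysis work, provided that onset dates can be taken from the hospital records. The planned collection of severity and duration implies such dates but does not guarantee them, and no adverse-event log is required. If they are not available, report length of stay by toxicity group descriptively, with deaths shown separately and no p-value. The landmark version ignores toxicities that begin later and drops earlier deaths. If the Swedish pattern held, a day-7 landmark would drop about 77% of the 18 to 27 one-month deaths expected among 180 patients (10% to 15%), or roughly 14 to 21.

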2.2.2 To assess incidence and severity of differentiation syndrome

2.2.3 To correlate outcomes with time to initiation of ATRA from diagnosis or suspicion of diagnosis.

2.2.4 To evaluate outcomes in academic and community centers separately.

2.2.5 To evaluate factors associated with outcome.

3. Selection of Patients

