3.1 Eligibility Criteria

- 3.1.1 All patients \geq 18 years of age who are **confirmed** to have a diagnosis of APL, which is defined as:
 - 3.1.1.1 Positive t(15:17) by FISH, OR
 - 3.1.1.2 Positive t(15:17) by conventional karyotype, OR
 - 3.1.1.3 Positive PML/RAR alpha by PCR
- 3.1.2 Patients must accept treatment and supportive care guidelines.
- 3.1.3 Referrals must be made as early as possible by treating physician (provider) but no later than 3 calendar days after ATRA or APL directed therapy is initiated. Consent can be obtained up until day 7 after initiating APL Directed Therapy.
- 3.1.4 Co-management can be started as soon as referral is made including weekends. The Physician at the NCORP community facility should make every effort to call the APL expert at the first suspicion of APL.

Rev. Add2

4. Registration Procedures

Rev. Add2

CTEP Registration Procedures

Food and Drug Administration (FDA) regulations and National Cancer Institute (NCI) policy require all individuals contributing to NCI-sponsored trials to register and to renew their registration annually. To register, all individuals must obtain a Cancer Therapy Evaluation Program (CTEP) Identity and Access Management (IAM) account (<https://ctepcore.nci.nih.gov/iam>). In addition, persons with a registration type of Investigator (IVR), Non-Physician Investigator (NPIVR), or Associate Plus (AP) (i.e., clinical site staff requiring write access to OPEN, RAVE, or TRIAD or acting as a primary site contact) must complete their annual registration using CTEP's web-based Registration and Credential Repository (RCR) (<https://ctepcore.nci.nih.gov/rrc>). Documentation requirements per registration type are outlined in the table below.

Documentation Required	IVR	NPIVR	AP	A
FDA Form 1572	✓	✓		
Financial Disclosure Form	✓	✓	✓	
NCI Biosketch (education, training, employment, license, and certification)	✓	✓	✓	
HSP/GCP training	✓	✓	✓	
Agent Shipment Form (if applicable)	✓			
CV (optional)	✓	✓	✓	

An active CTEP-IAM user account and appropriate RCR registration is required to access all CTEP and CTSU (Cancer Trials Support Unit) websites and applications. In addition, IVRs and NPIVRs must list all clinical practice sites and IRBs covering their practice sites on the FDA Form 1572 in RCR to allow the following:

- Added to a site roster
- Assigned the treating, credit, consenting, or drug shipment (IVR only) tasks in OPEN
- Act as the site-protocol PI on the IRB approval

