7.3 Statistical Analysis Plan

7.3.1 Primary Objective

One-month mortality rate will be estimated by dividing total number of deaths within one month of study entry by total number of cases with at least one-month follow up data. 95% RCI will be provided for this endpoint. We will also evaluate the OS data using the Kaplan-Meier plot.

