Compliance with treatment guidelines will be assessed as binary outcome and the successful compliance rate will be described with 95% confidence interval. A regression model will be developed to evaluate the factors associated with outcome. Data items such as age, risk status, comorbidity will be collected and evaluated.

Rev. Add2

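### Time to ATRA (objective 2.2.3) has only an unadjusted median-split analysis; the planned regression does not say that it will include the delay

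*Combined protocol and SAP*

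**What the plan says.** Section 2.2, objective 2.2.3, is "To correlate outcomes with time to initiation of ATRA from diagnosis or suspicion of diagnosis". The analysis specified for it is in Section 7.3.2: "The time from diagnosis and initiation of treatment will be assessed and dichotomized as" short or long, with the median as the cut. One-month mortality is compared by Fisher's exact test and overall survival by the log-rank test. On the starting point the section says: "In this analysis, the time of diagnosis will be determined by both: i) confirmed diagnosis date and ii) date of suspicious APL". Two origins and two outcomes make four comparisons, all reported with two-sided p-values. No covariate, stratification or quantitative use of the delay is mentioned, and nothing is said about values equal to the median.

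The last paragraph of 7.3.2 adds "A regression model will be developed to evaluate the factors associated with outcome" and "Data items such as age, risk status, comorbidity will be collected and evaluated". The outcome, the type of model and the delay are not named. That regression matches a separate objective, 2.2.5.

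Section 7.2 says that secondary endpoints will be treated mostly descriptively. No power is stated for the delay analysis.

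**The concern.** A median split treats all patients on the same side of the cut alike, so the size of the delay is lost. The documents expect few early deaths, so lost information is costly. Delay is also observed, not assigned. If it differs by age or risk group, an unadjusted comparison can report their effect as a delay effect, or hide a real one.

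Ties are a further gap. The communication log (Section 5.2.2 and Appendix II) holds dates. If delay is analysed in whole days (an assumption, since the case report forms are not in the documents), many patients may share the median value. The rule for ties then decides how unequal the groups are, and a rule of at or above the median can put everyone in one group.

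At stake is how well the trial can describe the link between delay and early death, which Section 1 names among the causes to be tackled.

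**Working it through.** **The plan's own figures.** Section 7.2 gives 180 eligible patients and repeated confidence intervals of 6-15.4% for 18/180 and 10.1-21.1% for 27/180. A Clopper-Pearson interval at the final O'Brien-Fleming critical value (1.977) gives 6.0-15.4% and 10.1-21.1%. These stand and are not in dispute.

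**Expected deaths.** Section 7.3.2 states "Overall the expected one-month mortality rate is in the range of 10-15% across all patients". So 0.10 × 180 = 18 and 0.15 × 180 = 27 deaths.

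**Planned test with equal halves.** Exact Fisher power for 90 vs 90, two-sided 0.05, with assumed odds ratios (OR) for long vs short:

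| Overall mortality | OR 2 | OR 3 |
|---|---|---|
| 10% | 7.0% vs 13.0%: power 21% | 5.4% vs 14.6%: 47% |
| 15% | 10.7% vs 19.3%: 30% | 8.4% vs 21.6%: 64% |

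**Comparison with an adjusted quantitative model.** Inputs: n = 180, mortality 12.5%, and one third high risk (the proportion in the Latin American cohort of Section 1.2). Assumed: death OR 3 for high risk and 1.5 per SD of age; delay = whole-day part of an exponential time with mean 1.0, 1.5 or 2.5. The share treated on day 0 is 1 - exp(-1/mean) = 63%, 49% or 33%. There were 3,000 trials per setting (Monte Carlo SE at most 0.9 points). Cells show power in %, Fisher with long = days > median / Firth logistic on log(1+days) adjusted for age and risk group:

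| Assumed effect (log-odds) | Mean 1.0 | Mean 1.5 | Mean 2.5 |
|---|---|---|---|
| 0.4 per day | 24.8 / 46.0 | 51.4 / 75.8 | 87.5 / 98.7 |
| Linear to 3 days, then flat | 23.2 / 36.5 | 35.5 / 49.9 | 41.7 / 50.6 |
| Step of 1.2 at 1 day | 66.8 / 63.8 | 39.3 / 54.9 | 19.9 / 34.6 |
| Step of 1.2 at 2 days | 19.5 / 42.4 | 50.2 / 55.7 | 61.1 / 55.2 |
| 0.8 × log(1+days) | 31.1 / 42.1 | 37.3 / 55.2 | 48.8 / 69.7 |

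The differences run from 55.2 - 61.1 = -5.9 to 75.8 - 51.4 = +24.4 points and are positive in 13 of 15 settings. Adjusting the split alone adds 2 to 6 points. Replacing it by log(1+days) in the adjusted model changes power by a further -11 to +19. For overall survival (mean 1.5, about 32 deaths, late deaths assumed), log-rank / adjusted Cox power in the same row order is 46/66, 29/37, 34/41, 45/45 and 34/43.

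**False rejection with no delay effect.** The ratio is the mean delay of the confounded group divided by that of the others.

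| Ratio | Risk group the only confounder: Fisher / adjusted log | Severity factor omitted from the model (30% prevalence, OR 3, mean 1.5): Fisher / adjusted log |
|---|---|---|
| 0.4 | 7.7-8.8 / 4.1-5.2 | 8.4 / 10.1 |
| 0.6 | 5.0-5.4 / 4.8-5.3 | 4.7 / 7.0 |
| 1.6 | 5.1-5.5 / 4.1-4.4 | 5.5 / 7.5 |
| 2.5 | 8.3-11.1 / 4.4-4.7 | 9.8 / 14.6 |

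The middle column spans the three means. The last column uses 2,000 trials; a run of 700 gave 9.0 / 11.1 at 0.4 and 7.7 / 16.1 at 2.5.

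**Ties.** A rule of days ≥ median leaves one group empty in about 100%, 33% and 0% of trials at means 1.0, 1.5 and 2.5. With days > median at mean 1.5, 54 of 180 patients are in the long group (5th to 95th percentile 42 to 90).

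**Confirmed-diagnosis origin.** If confirmation follows suspicion by 1, 2 or 3 days (assumed) and the mean delay from suspicion is 1.5 days, 1 - exp(-lag/1.5) = 49%, 74% or 86% of delays from confirmation are negative. Log(1+days) does not suit that origin.

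**The case against.** The regression's list of factors is open, and delay is a named interest of the trial, so the analyst may well include it. A reader might infer that the plan leaves delay out of the regression. The documents do not support that; they only fail to say that it is in. A reader might also infer that high-risk patients are treated sooner or later and that the planned tests are therefore biased. The documents show no such difference in either direction, and at ratios of 0.6 or 1.6 Fisher's test stays near 5%. No power is claimed for this analysis, so no stated property is broken. The 15 settings are chosen shapes and delays, not evidence from this trial.

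The strongest objection is to the remedy. The adjusted model holds near 5% when its only confounder is in the model. Appendix I lists other features that raise bleeding risk, such as active bleeding, renal failure and poor performance status. With one such factor omitted, the adjusted log model falsely rejects in about 10-16% at ratios 0.4 or 2.5, against about 8-10% for Fisher. A more sensitive analysis also picks up unmeasured confounding more readily. This stands, and it limits what may be claimed.

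The functional form is open too. The log model loses 3 to 6 points to Fisher (days > median) in two step settings. A split at days ≥ median beats it in two step-at-1-day settings: 44% vs 35% at mean 2.5, and about 61% vs 54% at mean 1.5 among trials with two non-empty groups.

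Finally, mortality counts the "total number of deaths within one month of study entry", and Section 3.1.3 says "Consent can be obtained up until day 7 after initiating APL Directed Therapy". Patients who die before consent are not in the data, and no adjustment repairs that.

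**Conclusion.** The point holds as a gap in a secondary analysis and is worth considering. The only analysis specified for objective 2.2.3 is an unadjusted median split without a tie rule, and the plan does not say that delay enters the regression. Under the assumed inputs, a quantitative adjusted term usually gains power (-6 to +24 points, 13 of 15 settings). It also removes confounding by risk group where imbalance is strong (Fisher about 8-11%, adjusted near 5%). Power stays modest in most settings, and 18 to 27 deaths allow only a weak check of functional form.

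Two wider conclusions do not follow. The primary endpoint and the sample size are untouched. The adjusted model does not show that delay causes death, since it controls only for what is measured and entered. The size of any benefit rests on assumed delays, effects and whole-day recording. Confidence in it is medium.

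**What to change.** In Section 7.3.2, state for objective 2.2.3:

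- The planned regression will include time to the first ATRA dose as a quantitative term, adjusted for age and risk group and reported as an estimate with a 95% CI. Use Firth-penalised logistic regression for one-month death, because deaths are few (18/3 = 6 to 27/3 = 9 per term), and Cox regression for overall survival.
- The main origin is first suspicion of APL, with log(1+days) as one reasonable prespecified form. For the confirmed-diagnosis origin, use untransformed days in the same adjusted model, because delay can be zero or negative.
- The short/long comparisons for both origins stay as supportive description, with long defined in advance as days > median. The reason is that this rule cannot leave a group empty when the median is the smallest value; it is not a claim of more power.
- Comorbidity, with its scoring stated, is added as a sensitivity adjustment.
- The result is interpreted as an association. The text names unmeasured severity, the weak check of functional form and deaths before consent as limits.

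The cost is a few sentences in the plan and a few lines of code, best settled before outcome data are analysed. Age, risk status and comorbidity are already to be collected. The sponsor should confirm that the case report forms hold the first ATRA date, because the log records only when APL therapy began. The price in the analysis is a loss of power if the true effect is a step near the median cut, and more sensitivity to factors left out of the model.

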1.1 Rationale for Proposed Study

Acute Promyelocytic Leukemia (APL) is a highly curable malignancy with most large cooperative group trials showing a survival above 90%. Patients entered in cooperative group trials are a highly selected group of patients and may not be a representation of outcomes in the general population. It is also likely that patients may not even be seen at a large treatment center due to the advanced nature of the disease and/or socioeconomic and distance constraints. However in recent years, data from single institutions as well as large population data bases show that approximately 1 in 3 patients diagnosed with APL die within the first month of diagnosis.⁽¹⁻⁵⁾ The first group to systematically analyze this is a population-based study from Sweden. All patients diagnosed with APL between 1997 and 2006 in the Swedish Adult Leukemia Registry were included in the study. A total of 105 patients with APL were diagnosed during that time and thirty (29%) of these patients died within 30 days of diagnosis with 23 of these 30 patients dying within the first week of diagnosis. The major cause of death was reported as bleeding, with differentiation syndrome, sepsis and multi-organ failure being other causes contributing to early mortality.⁽¹⁾

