Appendix II

APL Expert and NCORP Provider Communication

1. Date patient admitted -
2. Date APL suspected -
3. Date APL confirmed -
4. Date APL therapy started -
5. Date APL expert contacted -
6. Subsequent communications -

Date:

Date:

Date:

Date:

Date:

Date:

Date:

Date:

Date:

A Simplified Patient Care Strategy to Decrease Early Deaths in Acute Promyelocytic Leukemia (APL)

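### The short-versus-long time-to-treatment comparison counts deaths only from study entry, so where late-treated patients enter later, harm from delay may be attenuated or hidden

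*Combined protocol and SAP*

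**What the plan says.** Objective 2.2.3 relates outcome to the time from diagnosis, or suspicion of it, to ATRA. For this, 7.3.2 sets the exposure: "The time from diagnosis and initiation of treatment will be assessed and dichotomized as" short or long at the median. The starting date is taken in two ways: "i) confirmed diagnosis date and ii) date of suspicious APL". The outcome test is then: "One-month mortality rate will be compared in these two groups (short vs. long"), by Fisher's exact test. Overall survival is compared by logrank, with two-sided p-values.

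One-month mortality is defined once, in 7.3.1: "total number of deaths within one month of study entry by total number of cases with at least one-month follow up data". Section 7.3.2 gives no other time origin, no landmark and no delayed entry. Overall survival has no stated origin.

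Entry depends on several events. Section 4.5.1 allows consent only once APL is confirmed. Section 3.1.3 sets the outer limit: "Consent can be obtained up until day 7 after initiating APL Directed Therapy". Section 6 permits registration after treatment has begun but does not require that order. Appendix I allows ATRA before confirmation. On when patients die, Section 1.1 reports of the Swedish registry: "23 of these 30 patients dying within the first week of diagnosis".

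**The concern.** A patient has a time-to-treatment value only if alive at treatment, and contributes an outcome only if alive at study entry. For given confirmation and consent times, a longer delay can leave the required survival from suspicion unchanged or lengthen it, but cannot shorten it. If the long group enters later, its one-month window opens further down a steeply falling risk curve than the short group's window does.

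The mechanism therefore works in one direction. With no true effect, late-treated patients can look better; with real harm, the contrast moves toward no difference. Objective 2.2.3 examines the premise behind starting ATRA promptly, so a misleading null or reversed result would matter even in a secondary analysis. Adjusting for age, risk status or comorbidity in the planned regression does not correct for left truncation. Counting from the first dose does not either, since deaths during the delay would still be missing.

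**Working it through.** **Plan figure.** None is stated for this comparison. The Swedish rate reproduces: 30/105 = 28.6%, given as 29%.

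**Inputs from the documents.** 105 patients, 23 deaths in week 1 and 30 by day 30 (Section 1.1); expected one-month mortality 10-15% (7.3.2); 180 eligible (7.2), so about 90 per group after a median split.

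**Assumed, because the documents give no values.** Entry days, confirmation times, length of delay, and the true effect of delay.

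**Step 1: shape of the risk.**
- Days 0-7: −ln(82/105)/7 = 0.0353 per day.
- Days 8-30: −ln(75/82)/23 = 0.00388 per day, a ratio of 9.1.
- Scaling to 15% at day 30 multiplies both by ln(0.85)/ln(75/105) = 0.483, giving 0.0171 and 0.00187 per day.

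**Step 2: fixed entry days.** For entry on day e ≤ 7, one-month mortality from entry is 1 − exp{−[(7−e)h₁ + (23+e)h₂]}.
- e = 3: 4 × 0.0171 + 26 × 0.00187 = 0.117, so 11.0%.
- e = 5: 2 × 0.0171 + 28 × 0.00187 = 0.087, so 8.3%.

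| Entry day, short / long | No true effect: short vs long (odds ratio) | True hazard ratio 2 (true odds ratio 2.18) |
|---|---|---|
| 3 / 3 | 11.0% vs 11.0% (1.00) | 11.0% vs 20.9% (2.12) |
| 3 / 5 | 11.0% vs 8.3% (0.73) | 11.0% vs 15.9% (1.52) |
| 3 / 7 | 11.0% vs 5.5% (0.47) | 11.0% vs 10.6% (0.96) |

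The bias comes from the difference in entry days. With equal entry days it nearly vanishes.

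**Step 3: simulated entry.** Half the delays were uniform on 0-1 day and half on 1-4 days. Registration came 0-3 days after the gating event. Mortality was scaled to 15%, with no true effect of delay. Only patients alive at treatment and at entry were kept. Figures vary by about 0.01 between runs.

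| Confirmation after suspicion | Long/short ratio, entry after the later of confirmation and treatment | Long/short ratio, entry after confirmation alone |
|---|---|---|
| within 0-1 or 0-2 days | 0.79-0.84 | 0.91-0.93 |
| 1-3 days | 0.91 | 0.97 |
| 2-5 days | 0.97 | 1.00 |

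Under the first entry rule, a true hazard ratio of 1.3 appears as a mortality ratio of roughly 1.02-1.06 with confirmation in 0-2 days and 1.14-1.25 with slower confirmation. Without truncation it would be about 1.24-1.27.

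**Step 4: test of the remedy.** The delayed-entry rate ratio was stratified by time since suspicion.
- Risk set entered at registration, when registration can precede treatment: null ratio about 0.88-0.92 with confirmation in 0-2 days. This is no better than the uncorrected comparison, because the long label then depends on surviving to a later event.
- Risk set entered at the later of registration and treatment start: 0.99-1.01 under the null and 1.28-1.31 under a true 1.3, in every confirmation scenario.

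**The case against.** The strongest objection concerns the premise. A reader might infer that late-treated patients do enter later and that harm from delay is masked. The documents do not establish this. Entry is gated by confirmation and consent, and only the outer limit for consent moves with treatment start. A patient given ATRA at suspicion and one given it at confirmation could both be consented just after confirmation, on the same day after suspicion. This stands, and it is why the size is given as a range that reaches no bias.

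Second, the hazards come from a registry of all diagnosed patients counted from diagnosis, not from consented patients counted from suspicion. This also stands. The figures above are scaled to 15%, the upper end of the plan's expectation, but the shape of the curve is borrowed.

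Third, the practical effect is limited. A two-day entry gap moves one-month mortality by 2.6-2.8 points, against a standard error of about 5 points with 90 per group: √(0.10×0.90/90 + 0.127×0.873/90) = 4.7. Fisher's test has about 8% power for a hazard ratio of 1.3 even without bias. With no true effect and a biased 10% versus 12.7%, it favours delay significantly in about 6% of trials, against 1.6% without bias. Section 7.2 calls the secondary analyses mostly descriptive. This lowers the priority but does not remove the defect: the point estimate is still shifted, and low power does not correct a shift.

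Fourth, no analysis of enrolled patients recovers deaths that occur before entry. That is correct, and it has to be stated as a limit of the estimate.

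**Conclusion.** The concern holds in a conditional form. The plan compares groups defined by delay on an outcome counted from "total number of deaths within one month of study entry", with no allowance for left truncation, in a disease where risk falls about nine-fold after the first week. If this mechanism operates, it favours delayed treatment. Its size depends on entry and confirmation times that the documents do not give. With no true effect, the long/short mortality ratio is about 0.79-0.97 if entry follows the later of confirmation and treatment, and about 0.91-1.00 if it follows confirmation alone. It is small when confirmation is slow or entry days are equal.

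These figures rest on the assumed delays, the Swedish hazard shape and 15% 30-day mortality. They apply to the suspicion clock. The confirmed-diagnosis version was not sized; there, patients treated before confirmation have zero or negative times, which the plan does not address. The primary endpoint's stated figures are unaffected by this point.

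**What to change.** In 7.3.2:

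- **Suspicion-date version.** Replace Fisher's test and the ordinary logrank test with a left-truncated Cox model on a clock starting at the date APL was suspected, for death by day 30 and for overall survival. Each patient enters the risk set at the later of registration and start of APL-directed treatment.
- **Confirmed-diagnosis version.** Keep the planned short-versus-long comparison, apply the same delayed-entry rule, and place patients treated on or before confirmation in the short group.
- **Interpretation.** State that the estimate applies to patients alive at treatment and registration, that it assumes non-informative entry, and that deaths during the delay are not captured.
- **Data.** Appendix II already has a field for "Date APL suspected", with confirmation and therapy-start dates, but it is the log of contacts between NCORP providers and experts. Record the same three dates for lead-site patients, who may number up to 60.

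The cost is SAP wording, a standard delayed-entry option in the software, and three dates that 7.3.2 already needs. The statistical price is a slightly wider interval, because fewer patients are at risk in the first days.
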